6.2.3 Progression-free survival

Progression-free survival is defined as the interval between the date of first infusion and the earliest date of objective disease progression according to RECIST criteria v1.1 for patients with advanced or recurrent solid tumors, and based on RANO criteria for patients with recurrent or progressive GBM/high-grade glioma; or Investigator-confirmed clinical progression; or death due to any cause in the absence of progression. Patients who have not progressed or died at EOS will be censored at the time of their latest objective tumor assessment.

If a patient has no post-baseline objective tumor assessment then the PFS will be censored to 0 day.

Progression-free survival will be summarized for the FAP (Phase 1 portion of the study) by disease subgroup and dose cohort.

In the Phase 2a portion of the study (Simon's two-stage design), PFS will be summarized for the FAP and EEP. Median PFS and PFS at 6 months after start of study drug treatment (PFS6) will be assessed in the Phase 2a portion of the study (Simon's two-stage design), using KM method. The 95% CI will be calculated with Brookmeyer-Crowley method. The associated survival curve will be displayed.

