3.3 Number of patients

Up to 88 evaluable patients will be enrolled in the study.

The dose escalation portion of the study is completed. Dosed were 26 patients with advanced or recurrent solid tumors and 28 patients with recurrent or progressive GBM or high-grade glioma. In each of the groups 24 patients were evaluable for MTD assessment. Up to 34 evaluable patients with recurrent GBM whose tumor tissue is positive for EB1 and up to 6 evaluable patients with planned re-resection of recurrent GBM are expected to be treated in the expansion portion.

Assuming approximately 25% non-evaluability rate, up to 104 patients may be enrolled in total.

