5.3.3 End of Study visit

End of Study assessments are to be performed in patients who no longer receive BAL101553 treatment, and must take place within 7 days after the decision to discontinue treatment. Assessment will be performed in accordance with Table 8, or Table 9 for patients in the Phase 2a portion of the study.

Abnormal findings and clinically significant changes from baseline (Day 1 of Cycle 1) apparent from the physical examination will be recorded.

Vital signs (including BP) will be performed as described in Section 5.5.4. An ECG will be performed, as described in Section 5.5.5.

Transthoracal echocardiography will be performed as described in Section 5.5.6.

Laboratory safety tests (hematology, biochemistry, coagulation, cardiac troponin and urinalysis) will be assessed as described in Section 5.5.7.

Pregnancy testing must be conducted for women of child-bearing potential (see Section 5.5.7.6).

A blood sample for PK analysis will be collected, as described in Section 5.7.1.

In Phase 2a, a liquid biopsy for biomarker research should be obtained (see Section 5.8.1.2).

Radiology efficacy assessments must be repeated, if these have not been performed within the 35 days prior to the End of Study visit. Assessment of CA-125 or PSA in patients with non-measurable ovarian or prostate cancer must be repeated if these have not been performed within the 14 days prior to the End of Study visit. The assessment of cancer and the selection and reporting of radiological marker lesions or other assessment endpoints (CA-125 or PSA) are described in Section 5.6.

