5.6.3 Clinical progression

Patients who do not meet the criteria for progressive disease as described in Sections 5.6.1 and 5.6.2, but who exhibit signs and symptoms of clinical progression, will be considered for study purposes to have progressive disease.

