8.3.2.7 Progression-free and overall survival

Progression-free survival is defined as the interval between the date of first study drug administration and the earliest date of objective disease progression according to RECIST criteria v1.1 for patients with advanced or recurrent solid tumors, CA-125 Rustin criteria for ovarian cancer, PSA Working Group 2 criteria for prostate cancer; and based on RANO criteria for patients with recurrent or progressive GBM/high-grade glioma; or Investigator-confirmed clinical progression (see Section 5.6.3); or death due to any cause in the absence of progression. Patients who have not progressed or died at EOS will be censored at the time of their latest objective tumor assessment.

Overall survival is the time from first study drug administration to the date of death / or censored at the time the patient was last known to have been alive.

Progression-free survival will be listed for the FAP (Phase 1 portion of the study) by patient and dose group and by disease subgroup if appropriate.

In the Phase 2a portion of the study (Simon's two-stage design), OS and PFS will be calculated for the FAP and EEP. Median OS and PFS and the proportion of patients with PFS at 6 months after start of study drug treatment (PFS6) will be assessed in the Phase 2a portion of the study (Simon's two-stage design).

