Progression	Defined by any of the following: $\geq 25\%$ increase in sum of the products of perpendicular diameters of enhancing lesions compared with the smallest tumor measurement obtained either at baseline (if no decrease) or best response, on stable or increasing doses of corticosteroids*; significant increase in T2/FLAIR nonenhancing lesion on stable or increasing doses of corticosteroids compared with baseline scan or best response after initiation of therapy* not caused by comorbid events (eg, radiation therapy, demyelination, ischemic injury, infection, seizures, postoperative changes, or other treatment effects); any new lesion; clear clinical deterioration not attributable to other causes apart from the tumor (eg, seizures, medication adverse effects, complications of therapy, cerebrovascular events, infection, and so on) or changes in corticosteroid dose; failure to return for evaluation as a result of death or deteriorating condition; or clear progression of nonmeasurable disease.

 $\underline{Note} : All \ measurable \ and \ nonmeasurable \ lesions \ must \ be \ assessed \ using \ the \ same \ techniques \ as \ at \ baseline.$

MRI, magnetic resonance imaging; FLAIR, fluid-attenuated inversion recovery.

^{*} Stable doses of corticosteroids include patients not on corticosteroids.

Summary of the Proposed RANO Response Criteria

Criterion	CR	PR	SD	PD
T1 gadolinium enhancing disease	None	≥ 50% ↓	$< 50\% \downarrow \text{but} < 25\% \uparrow$	≥ 25% ↑*
T2/FLAIR	Stable or ↓	Stable or ↓	Stable or ↓	^*
New lesion	None	None	None	Present*
Corticosteroids	None	Stable or ↓	Stable or ↓	NA^{\dagger}
Clinical status	Stable or ↑	Stable or ↑	Stable or ↑	↓ *
Requirement for response	All	All	All	Any*

RANO, Response Assessment in Neuro-Oncology; CR, complete response; PR, partial response; SD, stable disease; PD, progressive disease; FLAIR, fluid-attenuated inversion recovery; NA, not applicable.

^{*}Progression occurs when this criterion is present.

[†] Increase in corticosteroids alone will not be taken into account in determining progression in the absence of persistent clinical deterioration.

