4.5 Pharmacokinetic analysis population(PK)

The PK analysis set includes all patients who received at least one dose of study drug and had at least one post-baseline PK assessment.

4.6 Efficacy-evaluable population (Phase 2a expansion portion of the study, Simon's two-stage design)

The efficacy evaluable population (EEP) is the subset of the FAP who had at least one post baseline RANO assessment after having received at least 6 weeks of study treatment.

For objective response rate and stage transition, the analysis will be based on patients with measurable disease at baseline in the EEP.

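### SAP 6.2.3 does not say whether day-0 censoring yields to death or clinical progression; read literally, it drops early failures without a scan from FAP PFS and PFS6

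*SAP*

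**What the plan says.** SAP 6.2.3 recognises three kinds of PFS event: objective progression, Investigator-confirmed clinical progression, and death from any cause without prior progression. Its general censoring rule is limited to patients without an event: "Patients who have not progressed or died at EOS will be censored at the time of their latest objective tumor assessment". A separate paragraph follows: "If a patient has no post-baseline objective tumor assessment then the PFS will be censored to 0 day". That sentence has no such limit, and no order of precedence is given.

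The protocol has the same events but no day-0 rule:

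- Section 8.3.2.7 counts as an event "or death due to any cause in the absence of progression" and censors only patients who have neither progressed nor died.
- Section 5.6.3 says that patients with signs and symptoms of clinical progression "will be considered for study purposes to have progressive disease", even when imaging criteria are not met.
- Appendix 6 (RANO) includes in its definition of progression "failure to return for evaluation as a result of death or deteriorating condition".

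SAP section 7, on changes from the protocol's planned analysis, declares none.

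PFS is summarised in the FAP and, for Phase 2a, also in the efficacy-evaluable population (EEP). The FAP needs only one partial dose (SAP 4.2). The EEP needs "at least one post baseline RANO assessment after having received at least 6 weeks of study treatment" (SAP 4.6), so the day-0 rule cannot reach anyone in it.

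**The concern.** A patient who dies in week 4 without a post-baseline scan is an event under the PFS definition and is censored at day 0 under the later sentence. Two competent programmers could therefore produce different FAP results from the same data.

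On the literal reading the error has one direction. A patient censored at day 0 leaves the risk set before the first event time and contributes nothing to the Kaplan-Meier estimate. The patients treated this way are the earliest failures, so median PFS and PFS6 both rise. FAP PFS also moves towards EEP PFS, although the FAP is the analysis that should show what the EEP's entry condition leaves out.

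PFS and PFS6 are among the main secondary endpoints of Phase 2a, and protocol 1.5.2.2.1 names OS and PFS as the primary endpoints of a possible later programme. Phase 1 is exposed too: FAP PFS is summarised there by dose cohort, and the cohorts have 3 to 8 patients (protocol Table 22), so one such patient is between 1/8 and 1/3 of a cohort. The trial is open-label and single-arm, so the rule should be settled before outcomes are in view.

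**Working it through.** **Can the case arise?** In Phase 2a the first scheduled scan falls in the last two weeks of Cycle 2, about Days 43 to 56. For patients who stop earlier, protocol 5.3.3 says: "Radiology efficacy assessments must be repeated, if these have not been performed within the 35 days prior to the End of Study visit". The baseline scan is taken 15 to 1 days before Day 1, so it can itself meet this condition until 35 - 15 = 20 to 35 - 1 = 34 days after Day 1. A patient who clinically progresses and stops in that window need not be scanned again. A patient who dies before a scan cannot be. So the case can arise.

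**Plan's own figure.** The documents state no assumed PFS and no expected number of unscanned failures. The only related figure is in protocol 3.3: "Assuming approximately 25% non-evaluability rate, up to 104 patients may be enrolled in total". It reproduces as 54 Phase 1 patients + (34 + 6) x 1.25 = 104. The same factor gives 34 x 1.25 = 42.5, so N = 43 in Phase 2a, of whom at most 43 - 34 = 9 are non-evaluable.

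**Formula.** Let s of N patients be progression-free at 6 months, let k fail before 6 months without a scan, and let there be no other censoring before 6 months.

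- Failures counted as events: PFS6 = s/N.
- Literal day-0 censoring: PFS6 = s/(N - k).
- Ratio: N/(N - k). With N = 43 this is 43/41 = 1.049 (k = 2), 43/38 = 1.132 (k = 5) and 43/34 = 1.265 (k = 9).

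**Illustration (assumed exponential PFS, N = 43).** The 6-month probability is 0.5^(6/median): 0.125, 0.25 and 0.354 for medians of 2, 3 and 4 months. Multiplied by 43 and rounded, s = 5, 11 and 15.

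| Assumed median | Events counted | k = 2 | k = 5 | k = 9 |
|---|---|---|---|---|
| 2 months | 5/43 = 11.6% | 5/41 = 12.2% | 5/38 = 13.2% | 5/34 = 14.7% |
| 3 months | 11/43 = 25.6% | 11/41 = 26.8% | 11/38 = 28.9% | 11/34 = 32.4% |
| 4 months | 15/43 = 34.9% | 15/41 = 36.6% | 15/38 = 39.5% | 15/34 = 44.1% |

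**Median PFS.** Take the expected order statistics of 43 exponential times with median 3 months, remove the k smallest, and take the median of the rest (midpoint when the number is even). The result is 3.05 months for k = 0, then 3.26, 3.59 and 4.07 months for k = 2, 5 and 9. This assumes that the unscanned patients are the earliest failures.

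**What does not move.** EEP PFS does not, because every EEP patient has a post-baseline assessment. The response rate, the stage decision and OS do not, because none of them uses this rule.

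**The case against.** The strongest reply is that the sentence is a fallback. The sentence before it censors event-free patients at their latest objective assessment. For a patient with no post-baseline scan, that would be the baseline scan, taken before Day 1, and would give a negative time; day 0 fills that gap. Read so, the rule only makes protocol 8.3.2.7 workable, there is no bias, and section 7 needs little more than a note. This reading is plausible and may be what was intended, but the text does not say so, and as written the sentence covers everyone without a scan.

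The upper figures can also be challenged. k = 9 needs every non-evaluable patient to be an unscanned failure, although non-evaluability also covers early stopping for toxicity or withdrawal. With a median of 4 months, the expected failures by Day 34 are 43 x 0.176 = 7.6, so k = 9 would need further unscanned failures after the waiver window. Eligibility also requires a life expectancy of at least 12 weeks and neurological stability, and N = 43 assumes full enrolment. These points stand: k = 9 is a ceiling, not an expectation.

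A site may record RANO progression when a patient fails to return through deterioration, and SAP 5.1 takes the response as reported in the CRF. Whether such a patient has an objective assessment for the day-0 rule is unsettled, which is a further reason to state the precedence.

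Finally, no hypothesis test or decision rule rests on PFS. That limits the consequence but does not remove the ambiguity.

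**Conclusion.** The concern holds. SAP 6.2.3 contains a rule that, followed as written, contradicts its own event definition, protocol 8.3.2.7 and 5.6.3, and the RANO definition in Appendix 6. The effect is zero if the sentence is confined to event-free patients. On the literal reading, FAP PFS6 is inflated by N/(N - k), which is a factor of 1.05 to 1.26 for k = 2 to 9 at N = 43. The direction is certain as soon as one such failure occurs and some patients remain progression-free at 6 months. The size is not known, because it rests on an assumed N, an assumed exponential PFS, no other censoring before 6 months, and a k that the documents do not give. The point is confined to FAP PFS and PFS6 in Phase 2a and FAP PFS in Phase 1. It should be corrected before database lock.

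**What to change.** Replace the day-0 sentence in SAP 6.2.3 with:

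> *Patients with no post-baseline objective tumor assessment who die or have Investigator-confirmed clinical progression are counted as PFS events on that date. Day-0 censoring applies only to patients with no post-baseline assessment and no such event.*

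Failure to return because of death or deterioration is then covered by one of the two named events. A death long after treatment, in a patient never scanned, counts on its own date, as protocol 8.3.2.7 already implies.

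List the day-0 rule in SAP section 7 as an addition to the protocol. The cost is one sentence and one line. No new data are needed: deaths are already collected for OS, and clinical progression is already a PFS event. If the sponsor always meant the fallback reading, the new wording simply records it.

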6.2.4 Overall Survival

Overall survival is the time from first study drug administration to the date of death / or censored at the time the patient was last known to have been alive.

Overall survival will be summarized using KM method for the FAP (Phase 1 portion of the study) and the FAP and EEP for the Phase 2a portion of the study (Simon's two-stage design).

6.3 Safety analysis

Safety assessments will be conducted throughout the entire study period. Analyses will be performed using safety population, unless otherwise specified.

The safety evaluations will include analyses of AEs, laboratory assessments (hematology, biochemistry, cardiac troponin, coagulation, urinalysis), pregnancy testing in women of childbearing potential, ECG, transthoracal echocardiography, chest X-ray / CT / MRI, vital signs, ECOG performance status, physical examination, and evaluation of concomitant medications.

6.3.1 Treatment exposure and compliance

The duration (in days) of BAL101553 exposure will be listed and summarized using descriptive statistics.

The actual dose of BAL101553 received and study drug dose interruptions and reductions will be listed and summarized using descriptive statistics.

Study drug compliance will be calculated as: $100 \times [(\text{total dose received})]/(\text{sum of total planned dose for each dosing period, excluding period of interruption due to AE})$.

Study drug compliance will be summarized using standard summary statistics by disease subgroup and dose cohort. Study drug compliance will also be summarized in categories "<80%", "≥80%-≤125%" and ">125%" using frequency tables.

6.3.2 Dose-limiting toxicity

The dose limiting toxicities will be listed and will be summarized for each disease subgroup and dose cohort from part I using the MTD determining population.

The MAD is defined as the dose level at which DLT are observed during treatment Cycle 1 in \geq two of (up to) three patients with DLT in the first three patients of a dose cohort, or \geq two of (up to) six patients with DLT in a dose cohort that was expanded to six patients and at which dose escalation is being stopped.

The MTD is defined as the highest dose level below the MAD with an acceptable tolerability profile.

The MTD may be different for patients with advanced or recurrent solid tumors and for patients with recurrent or progressive GBM/high-grade glioma.

6.3.3 Adverse events (AEs)

AE tables and listings will display only treatment-emergent AEs. Any non-treatment-emergent AE will be displayed on a separate listing.

Treatment-emergent events are defined as all events occurring after BAL101553 treatment begins, up to 28 days after last study drug administration. Any AE starting prior to first treatment on Cycle 1 Day 1, or more than 28 days after last study drug administration will be considered as non-treatment emergent. The relationship of an AE to treatment is recorded as unrelated, unlikely, possible and probable. For analysis purposes, 'related' AEs will be those reported as possibly related or probably related, or those for which the relationship is unknown.

AEs will be presented in data listings including dose cohort, disease subgroup, patient, dates/times of event, MedDRA SOC, PT, duration of the event, seriousness, CTCAE grade, intensity, drug adjustment, treatment taken, relationship to study drug and outcome.

An overview table (including only treatment-emergent AEs) will be also presented with the number (and percentage) of patients with:

- At least one AE
- At least one related AE
- CTCAE grade 3/4 or severe AEs
- CTCAE grade 3/4 or severe related AEs
- At least one SAE
- At least one related SAE
- AEs leading to dose modifications (i.e. dose reduced or dose interruption)

- Related AEs leading to dose modifications (i.e. dose reduced or dose interruption)
- AEs leading to study drug discontinuation
- Related AEs leading to study drug discontinuation
- AEs leading to death.
- Related AEs leading to death.

The number of events will be also included in this overview table. This table will be displayed by disease subgroup and dose cohort for all the study period.

All treatment-emergent AEs and treatment-emergent AEs related to treatment will be summarized by incidence rate tables broken down by:

- SOC and PT.
- SOC, PT and worst CTCAE grade/intensity.
- SOC, PT and worst CTCAE grade/intensity.
- SOC, PT and drug relationship.

The incidence rate table for treatment-emergent AEs and treatment-emergent AEs related to treatment by SOC, PT and worst CTCAE grade/intensity will be repeated by treatment cycle using the actual dose received within each cycle.

In addition, all treatment-emergent AEs and treatment-emergent AEs related to treatment will be summarized by SOC, PT and

- Worst CTCAE grade and cycle of occurrence of first event.
- Worst CTCAE grade during cycle 1 and during study.

Treatment-emergent AEs leading to dose modifications and leading to study drug discontinuation will be also summarized by SOC and PT.

6.3.4 Laboratory evaluation

Laboratory safety assessments include hematology, biochemistry, cardiac troponin, coagulation and urinalysis.

The laboratory tests for safety analyses consist of the following:

- Hematology: Hemoglobin (Hb), hematocrit (Hct), red blood cell (RBC) count, platelet count and total and differential white blood cell (WBC) count (neutrophil including bands, lymphocyte, monocyte, eosinophil and basophil counts).
- Biochemistry: Serum creatinine, blood urea nitrogen (BUN), uric acid, sodium, potassium, chloride, bicarbonate, magnesium, calcium, inorganic phosphorus, glucose, albumin, total protein, Aspartate amino transferase (AST), Alanine amino transferase (ALT), total bilirubin, alkaline phosphatase (AP), lipase, lactate dehydrogenase(LDH) and creatine phosphokinase (CK).
- Cardiac troponin: Either troponin T or troponin I.
- Coagulation: International normalized ratio (INR) for reporting prothrombin time and activated partial thromboplastin time (APTT).

- Urinalysis: Dipstick analysis for specific gravity, glucose, protein, and blood. Microscopic analysis for white blood cells, RBCs and any additional findings (such as casts).
- Pregnancy test (at screening, D1 of every cycle): Serum or urine test for human chorionic gonadotropin (hCG).

Laboratory values will be converted into SI units and the severity grade determined based on CTCAE v5.0 whenever applicable.

The laboratory parameters will be presented in data listings sorted by disease subgroup, dose cohort, patient, study day, study time and analyte. Out-of-range values will be flagged with h (high) or l (low). Out-of-marked-range values (defined by Basilea SOP LIS-GLO-000412 Preferred Units and Marked Factors) will be flagged with H (marked high) or L (marked low).

Descriptive statistics for each laboratory analyte at each assessment time will be tabulated. The change from baseline will be also summarized.

An analysis of individual patient changes by disease subgroup dose and cohort will be given using shift tables showing the change from CTCAE grade/intensity at baseline to the worst CTCAE grade/intensity (including unscheduled assessments) during the study.

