3.4 Study centers

Four investigational centers participated in the dose escalation portion designed to characterize the MTD, and up to twenty investigational centers will participate in the expansion portion in patients treated at the RP2D.

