- 11. Blood pressure (BP) combination treatment with more than two antihypertensive medications.
- 12. Any history of cerebral hemorrhage, cerebral aneurysm, or ischemic stroke; or a history of transient ischemic attack within 24 months prior to screening in patients with advanced or recurrent solid tumors.

Acute intratumoral hemorrhage in patients with recurrent or progressive GBM or high-grade glioma, considered by the study Investigator to be clinically significant.

- Patients with MRI or CT demonstrating old hemorrhage or subacute bleed after a neurosurgical procedure (biopsy or resection) will be eligible for treatment.
- 13. Significant cardiac disease or abnormality, including any one of the following:
 - Left ventricular ejection fraction < 50% at screening (assessed by echocardiography).
 - QTcF > 470 ms on screening electrocardiogram (ECG) or a clinically relevant ECG abnormality.
 - Congenital long QT syndrome.
 - History of sustained ventricular tachycardia, ventricular fibrillation or torsades de pointes.

- Presence of atrial fibrillation with tachyarrhythmia (ventricular response rate > 100 bpm).
- Bradycardia (heart rate < 50 bpm).
- Complete left bundle branch block.
- Bifascicular block (complete right bundle branch block and anterior or posterior left hemiblock).
- Myocardial infarction, acute coronary syndrome (including unstable angina), coronary revascularization procedures, or coronary arterial bypass grafting within 6 months prior to starting study drug.
- Cardiac troponin (either troponin T or troponin I) above institutional ULN.
- Congestive heart failure of New York Heart Association class III or IV.
- 14. Uncontrolled intercurrent illness that would unduly increase the risk of toxicity or limit compliance with study requirements in the opinion of the Investigator; including but not limited to: ongoing or active symptomatic infection, uncontrolled diabetes mellitus, unstable or uncompensated cardiac, hepatic, renal, respiratory, or psychiatric illness.
- 15. Current anticoagulation with warfarin potassium or other coumarin derivates. Heparin/low-molecular weight heparin (at prophlylaxis or treatment doses), aspirin or other oral platelet inhibitors are permitted.
- 16. Women who are pregnant or breast-feeding. Men or women of reproductive potential who are not willing to apply effective birth control during the study and for at least 30 days after the last dose of study drug in both sexes.

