5.5.7 Laboratory parameters

The laboratory safety tests include hematology, biochemistry, cardiac troponin, coagulation and urinalysis as per schedule of assessments (see Table 8 or Table 9). Additional testing may be performed whenever clinically indicated at the discretion of the Investigator. All samples for a given study center must be analyzed by the same local laboratory throughout the study, as designated by the Investigator. The results are to be printed, signed and dated by the Investigator or his/her designee.

In the event of unexplained abnormal laboratory test values, the tests must be repeated immediately and followed-up until return to the normal range, stabilization, and/or until an adequate explanation of the abnormality has been determined. When a clear explanation is established this must be recorded in the CRF. Abnormal laboratory results should not be recorded as an AE unless the abnormality is associated with a clinically relevant condition.

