5.5.7.3 Cardiac troponin

The schedule for cardiac troponin blood samples is described in Table 8 or Table 9. Cardiac troponin must be performed and reviewed within 72 h of the first administration of BAL101553 on Day 1 of Cycle 1. Cardiac troponin must also be performed and reviewed within the 24 h prior to administration of BAL101553 on Days 8, 15 and 22 of Cycle 1, on Days 1 and 15 of Cycle 2, and in Phase 1 also on Days 8 and 22 of Cycle 2.

The use of either cardiac troponin-I or troponin-T is permitted; however, the same troponin test must be used consistently for a given patient at Screening and throughout the study.

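### Troponin means and mean changes in SAP 6.3.4 average raw values from different local assays; scaling to the local ULN, with counts above it, would make the tables readable (minor)

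*SAP*

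**What the plan says.** **Measurement.** Protocol 5.5.7.3 leaves the choice of test to the site: "The use of either cardiac troponin-I or troponin-T is permitted". Within a patient the choice is fixed: "the same troponin test must be used consistently for a given patient at Screening and throughout the study". Testing is local, under Protocol 5.5.7: "All samples for a given study center must be analyzed by the same local laboratory throughout the study". Protocol 3.4 adds that "up to twenty investigational centers will participate in the expansion portion in patients treated at the RP2D". Eligibility uses each institution's own limit; exclusion criterion 13 in Protocol 4.3 reads "Cardiac troponin (either troponin T or troponin I) above institutional ULN".

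**Analysis.** SAP 6.3.4 has one troponin line: "Cardiac troponin: Either troponin T or troponin I". For laboratory data in general it states: "Descriptive statistics for each laboratory analyte at each assessment time will be tabulated. The change from baseline will be also summarized". SAP 6 includes the mean among the descriptive statistics and combines data from all centers. The only harmonisation in SAP 6.3.4 is conversion to SI units and CTCAE v5.0 grading where that applies. It states no scaling to the local ULN and no split by assay.

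**Other outputs.** SAP 6.3.4 also plans listings with out-of-range and marked out-of-range flags, and shift tables from baseline grade to worst grade. SAP 6.3.3 plans AE tables by preferred term and worst grade. Protocol 8.3.2.8 plans a frequency table of laboratory abnormalities by worst grade, dose level and cycle, and a listing of newly occurring abnormalities.

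**The concern.** A mean across patients is meaningful only if the values share a scale. The protocol does not treat troponin results as sharing one: it holds each patient to a single test and judges eligibility against the institution's own limit. Converting to SI units changes the unit of a result but does not remove a difference in reading level between two assays. The planned tables can therefore average values that are not comparable, and the result depends on which laboratories the patients happen to use.

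Troponin is a parameter of interest in this program. Myocardial injury is among the DLTs of the 2-hour IV study (Protocol Table 2). Drug-related troponin increase was recorded in 2 of 7 solid-tumor patients at 20 mg/day, one at grade 1–2 and one at grade 3–4 (Protocol Table 25). An external cardiologist sits on the Phase 2a safety committee (Protocol 3.1.3). A group-level troponin table should be readable, and at stake is whether this one is.

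**Working it through.** The documents give no troponin values, assay limits or T/I split, so there is no figure in the plan to reproduce. The check has three steps.

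**1. What is averaged under each reading of the SAP.** If T and I share a table, values from two tests and several laboratories are averaged. If they are tabulated separately, values from several local laboratories are still averaged within each table. Averaging across local assays in raw units occurs under both readings; averaging T with I occurs only under the first.

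**2. Effect on mean change from baseline (illustration; all inputs assumed).** Suppose every patient's change has mean 0.5 × ULN and SD 0.5 × ULN. A share w of patients is on assay A (ULN = 1 raw unit) and the rest on assay B (ULN = s raw units).

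- Pooled raw mean: m = 0.5 × [w + (1 − w)s]
- Mean square: e = (0.5² + 0.5²) × [w + (1 − w)s²] = 0.5 × [w + (1 − w)s²]
- Pooled SD: √(e − m²)
- Share of the pooled mean supplied by assay A patients: w / [w + (1 − w)s]

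Worked case, s = 10 and w = 0.5: m = 0.5 × 5.5 = 2.75; e = 0.5 × 50.5 = 25.25; SD = √(25.25 − 7.5625) = 4.21; mean/SD = 0.65; share from A = 0.5/5.5 = 9%.

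| s | Mean/SD, 50:50 | Share from A, 50:50 | Mean/SD, 80:20 | Share from A, 80:20 |
|---|---|---|---|---|
| 1 | 1.00 | 50% | 1.00 | 80% |
| 2 | 0.90 | 33% | 0.90 | 67% |
| 5 | 0.73 | 17% | 0.62 | 44% |
| 10 | 0.65 | 9% | 0.48 | 29% |
| 30 | 0.60 | 3% | 0.38 | 12% |

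On the × ULN scale, mean/SD is 1.00 in every row. The loss comes entirely from averaging in raw units.

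**3. Effect of a changing assay mix (illustration, absolute means only).** Suppose each patient stays at 0.5 × own ULN and one test's ULN is k times the other's. The pooled mean is 0.5w + 0.5(1 − w)k. Moving from 50:50 to 30:70 gives:

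- k = 1.5: 0.625 to 0.675, +8%
- k = 2: 0.75 to 0.85, +13%
- k = 3: 1.00 to 1.20, +20%

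This does not carry over to the change table. With no patient changing, every change is zero, and so is the mean change for any mix and any k. The shift is also large. If no one on the other test leaves, the remaining fraction on the shrinking test is 30/70 = 3/7, so 57% of that group must leave. In Phase 2a, scheduled troponin before the End of Study visit stops at Cycle 2 Day 15 (Protocol 5.5.7.3 and Table 9), six weeks after Cycle 1 Day 1.

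**The case against.** **A reader might infer that the SAP treats T and I as one test and will pool them.** The documents do not support that. The tables are specified by analyte ("Descriptive statistics for each laboratory analyte at each assessment time will be tabulated"), the listings are sorted by analyte, and the troponin line can be read as a category heading like the one for coagulation. Pooling T with I is a possibility left open by the wording. This objection stands, but averaging across local assays remains either way.

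**Individual rises remain visible.** This also stands. Range flags attach to single results, shift tables use the worst grade including unscheduled samples, and each patient's own change is measured with one test. The two Phase 1 troponin cases reached the AE tables with grades. These routes have limits. Protocol 5.5.7 and 7.1.1 keep laboratory abnormalities without clinical relevance out of AE reporting. Shift tables give no timing and apply only where grading does. Flags are not counted by visit.

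**The protocol already promises abnormality counts by cycle.** Protocol 8.3.2.8 does, and SAP 7 reports no change from the protocol. SAP 6.3.4 does not carry that table over, although SAP 6.3.5 and 6.3.6 plan counts of out-of-range values for vital signs and QT/QTc. The promise lessens the concern but leaves the troponin output to be written into the SAP.

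**The cardiac background is indirect.** The myocardial injury DLT arose with the 2-hour infusion, and Protocol 1.4 states that daily oral dosing is not associated with vascular toxicity. The Table 25 cases were solid-tumor patients; Table 24, which covers GBM/high-grade glioma and lists terms seen in more than one patient, shows no troponin term. This is fair, and it supports a low rating.

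**Conclusion.** The concern holds as a minor point of safety reporting. Followed as written, the plan averages raw troponin values from different local assays. The mean and mean-change tables will be hard to interpret and weighted toward the higher-reading assays. The size cannot be determined from the documents: across the assumed scale ratios of 2 to 30, the mean/SD ratio falls from 1.00 to between 0.90 and 0.38. If all laboratories happened to read on the same scale, nothing would be lost. The mix-shift percentages illustrate absolute means only.

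Two stronger readings are not supported. One is that a cardiac signal would be hidden: the individual-level outputs are unaffected, and no endpoint, eligibility decision or stated dosing rule uses these means. The other is that every value above ULN must be new because entry requires a value within the limit. The exclusion applies at screening, whereas SAP 5.1 takes baseline as the last pre-dose assessment, so a baseline above ULN is not ruled out and any count must be conditioned on baseline.

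**What to change.** In SAP 6.3.4:

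1. State that troponin T and troponin I are not pooled in raw units.
2. Summarise troponin values and change from baseline as multiples of the reporting laboratory's ULN.
3. As the main table, show by visit the number tested and the number (%) above local ULN. Combine T and I on this scale, and separate patients at or below ULN at baseline (last pre-dose value) from those already above it.
4. Keep raw values, with the test named, in the listings.

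The cost is SAP wording and one extra table. Local limits are already needed for exclusion criterion 13 and for range flags. If T and I are also shown separately, the groups will be small, with up to 34 evaluable patients in Phase 2a; that is why the combined count should be the main display.
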